11. STUDY MONITORING, AUDITING, AND DOCUMENTATION

During or after the clinical trial ends, regulatory authorities, the IRB, and/or representatives of the Investigator may request access to all source documents, CRFs and other protocol documentation for on-site audit or inspection.

11.1. Data and Safety Monitoring Board

The Data and Safety Monitoring Board (DSMB) for this clinical trial will be comprised of an independent group of experts that will be established to ensure the safety of participants and the integrity of the data. The DSMB will regularly review study data to monitor participant safety, study conduct, and progress, and will make recommendations regarding the continuation, modification, or suspension of the trial.

DSMB will be comprised of individuals with relevant clinical expertise and an unblinded biostatistician and also may include pharmacologists, patient advocates, etc.

CONFIDENTIAL

A DSMB Charter will be developed; it will detail the DSMB's operational procedures and oversight responsibilities including:

- The roles and responsibilities of DSMB members
- The frequency and format of DSMB meetings
- The process for reviewing safety and efficacy data
- The criteria for discontinuing the trial
- The communication plan between the DSMB, the Sponsor, and the IRB.

All DSMB members will disclose any potential conflicts of interest and will be free from significant conflicts that could impact their objectivity. Members with conflicts of interest will recuse themselves from DSMB activities if deemed necessary.

12. STATISTICAL CONSIDERATIONS

A statistical analysis plan (SAP) will be developed prior to the beginning of participant recruitment that will detail the intended statistical methods that will be used to evaluate the primary, secondary and exploratory endpoints.

12.1. General Considerations

The proposed study is an open-label Phase I investigation intended to gather data on the safety, PK profile and preliminary efficacy of whole organic psilocybin mushrooms in patients suffering from PTSD.

The statistical analysis plan (SAP) will be finalized prior to database lock. The SAP will include a more technical and detailed description of the statistical analyses described in this section. This section is a summary of the planned statistical analyses of the most important, primary and secondary, endpoints.

Continuous variables will be summarized by descriptive statistics (number of cases, mean, and standard deviation, median, Q1, Q3, minimum, and maximum). Categorical variables will be summarized using counts of patients and percentages.

All analyses will be performed on patients who were administered the study drug (data on screen failure patients will be listed only).

12.2. Sample Size

A sample size of up to 24 treated participants was selected because it is believed to provide sufficient data to determine whether psilocybin mushrooms are safe for this PTSD patient population.

12.3. Analyses of Safety

Quantitative safety analyses will examine AEs, clinical laboratory parameters, physical examinations, concomitant medications, suicidal ideation, and psychiatric health. All assessments will be presented in data listings.

Treatment-emergent adverse events (TEAEs) are defined as any adverse events that develop

CONFIDENTIAL

after initiation of treatment, or any event already present that worsens following exposure to treatment.

Number and percentage of patients with TEAE will be summarized by primary system organ class and preferred term. Separate summaries will be done, at minimum, for all TEAEs, serious TEAEs, related TEAEs, severe TEAEs and TEAEs by CTCAE grade.

Continuous parameters will be summarized descriptively by visit including observed values and change from baseline.

12.4. Analyses of Secondary Objectives

Non-compartmental analyses will be used to measure derived PK parameters for psilocin including AUC_{0-t} , $AUC_{0-\infty}$, T_{max} , C_{max} and $t_{1/2}$ (and perhaps others). The PK profile of psilocin will be listed and presented graphically. PK parameters of psilocin will be summarized descriptively.

12.5. Analyses of Exploratory Objectives

The following is an outline of the planned analyses to be done for various exploratory objectives (and associate endpoints).

- Analyses of changes from baseline for continuous questionnaires will be summarized descriptively by visit. and analyzed using repeated measures ANCOVA or generalized linear mixed modeling, as described in the SAP. The statistical significance of the change from baseline ($p < 0.05$) will be determined for each measure. 95% confidence intervals will also be derived.
- Change in average sleep duration, sleep latency, sleep efficiency, sleep timing, sleep consistency, nightly heart rate variability, and daily steps from baseline (through product use) will be assessed, as measured by the health tracking wearable device.

As heart rate and heart rate variability are highly confoundable metrics, analysis of these metrics will be done on all data collected but limited to days without unusual conditions reported by the participants (e.g., unusual alcohol consumption, changes in medication, very high activity, illness, death of a family member or other extraordinary stress unrelated to study participation).

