4.4.3 Exploratory Endpoints

Exploratory endpoints will be driven by a fundamental analysis of mean changes in clinician rating scales and patient QoL and PRO instruments compared from baseline to one or more visit timepoints. Mean changes in epigenetic markers also will be assessed. In addition, data captured by the health tracking wearable device will be assessed. For all exploratory endpoints, appropriate statistical methods will be employed as described, more generally in Section 13.5. A formal outline of the statistical methods to be employed will be detailed in the SAP.

- At Screening, participants will confirm that they have had a traumatic event, captured in the LEC-5 and that they have a minimum score of at least 33 as determined the PCL-5, respectively.
- Mean changes from baseline to various study visit timepoints (e.g., Study Day 7) will be calculated for the following instruments:
 - General Anxiety Disorder 7 Item Scale (GAD-7)
 - Patient Health Questionnaire-9 (PHQ -9)
 - Healing Experience of All Life Stressors (NIH HEALS)
 - Brief Pain Inventory (BPI)
 - Columbia-Suicide Severity Rating Scale (C-SSRS)

CONFIDENTIAL

- Profile of Mood States (POMS)
- Sheehan Disability Scale (SDS)
- Watts Connectedness Scale (WCS)
- Mystical Experience Questionnaire-revised (MEQ30)
- Challenging Experience Questionnaire (CEQ)
- 5-Dimensional Altered States of Consciousness Rating Scale (5D-ASC)
- Alcohol Use Disorders Identification Test (AUDIT)
- Drug Use Disorders Identification Test (DUDIT)
- Mean changes in epigenetic markers from baseline to various timepoints will be calculated for psychiatric and cardiovascular genes.
- Data collected by a health tracking wearable device such as nightly sleep duration, sleep latency, sleep efficiency, heart rate and heart rate variability during sleep, and daily steps will be calculated.

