Study Medication Administration

Provided the participant remains eligible, they will undergo a symbolic ceremony in which intentions are set and then be instructed to self-administer the study drug.

- The participant will self-administer, under observation, a whole, dried, ground organic psilocybin mushroom (RTT1121 also called JMF-01) which has been milled and formulated into 3 solid chocolates.
 - A physician will be onsite, or if observing via video conferencing can reach the study site within 10 minutes in case of a medical emergency.

Post-Dose Monitoring and Assessments

Following the self-administration of the single dose of study drug, participants will be instructed to lie down wearing eyeshades and listen to a preselected music playlist via headphones and speakers. Participants will be closely monitored for medical and psychological (including psychosis) adverse effects to ensure their safety and well-being. Participants also will be assessed via clinician rating scales.

In addition to the therapists (and group) support provided, a trained therapy dog also will be available in the dosing room to offer additional support, if requested by the participant.

- Vital signs are to be measured every 30 minutes for at least 8 hours following study drug administration.
 - If vital signs are abnormal at 8 hours, the participant will remain at the study site for continued observation until the measurements return to baseline values, or the Investigator deems that not further monitoring is needed. Vital sign measurements listed below may be considered abnormal; (however, the Investigator may override these values):
 - Blood pressure above 140/90 mmHg
 - Heart rate outside the range of 50-90 beats per minute
 - Respiratory rate
 - Pulse oximetry – SpO2 ratio $< 92\%$
- Blood samples for PK profiling will be collected at the following timepoints
 - 30 minutes (± 2 mins)

CONFIDENTIAL

- 60 minutes (± 5 mins)
- 90 minutes (± 5 mins)
- 120 minutes / 2 hours (± 5 mins)
- 4 hours (± 15 minutes)
- 8 hours (± 15 minutes)
- Manage participant's complaints of pain and administer pain medication as warranted and record the type(s) and amount(s) administered.
- Nearing the 8-hour timepoint, the following clinician rating scales and participant QoL and PRO instruments should be administered and/or completed by the participant, respectively:
 - GAD-7
 - PHQ-9
 - C-SSRS
 - MEQ30-revised
 - CEQ
 - 5D-ACS
 - WCS
 - BPI

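### Section 12.5 fixes a p<0.05 significance verdict for each continuous questionnaire in an uncontrolled trial of up to 24, without saying that these p-values are nominal

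*Protocol*

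**What the plan says.** Section 12.5 gives the rule for the continuous questionnaires: "The statistical significance of the change from baseline" is to be determined separately for each measure, with p<0.05 as the threshold. It adds that "95% confidence intervals will also be derived". The modelling is deferred: changes will be "analyzed using repeated measures ANCOVA or generalized linear mixed modeling, as described in the SAP". The p<0.05 rule is not deferred; it stands in the protocol. The by-visit wording belongs to the descriptive part: "Analyses of changes from baseline for continuous questionnaires will be summarized descriptively by visit".

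Section 4.4.3 sets the scope: "Mean changes from baseline to various study visit timepoints (e.g., Study Day 7) will be calculated for the following instruments". Thirteen instruments follow: GAD-7, PHQ-9, NIH HEALS, BPI, C-SSRS, POMS, SDS, WCS, MEQ30, CEQ, 5D-ASC, AUDIT and DUDIT. The visits to be compared with baseline are left open.

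Section 4.1 describes one open-label arm with no control group, and Section 12.2 sets up to 24 treated participants. The primary endpoints (Section 4.4.1) and the pharmacokinetic endpoints (Section 12.4) are to be described, with no significance threshold.

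**The concern.** The protocol keeps its primary and secondary analyses descriptive and attaches a significance verdict only to the exploratory tier, where the evidence is weakest. Two separate problems follow.

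- **Many verdicts.** Each measure gets its own 5% test. The chance that some scale is called significant when none has changed is therefore well above 5%.
- **No comparator.** The tested hypothesis is that the mean change is zero, which is not the same as no drug effect. Time, expectancy, psychological support or regression to the mean can move a scale, and a correct rejection would still receive the same label.

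At stake is how an exploratory result is worded and read. Section 2.2 intends the results to inform larger randomized trials and to reach physicians, patients and regulators, so the label significant would carry weight that the design cannot support.

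**Working it through.** The protocol states no family-wise error rate, power or effect size, so it has no figure of its own to reproduce. The only stated error rate is 0.05 per measure. Two-sided tests are assumed, in line with the 95% intervals.

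**Step 1: which instruments have a baseline.** WCS, MEQ30, CEQ and 5D-ASC are first given after dosing. In Section 7.1.4 they appear only in the list that begins "Nearing the 8-hour timepoint, the following clinician rating scales and participant QoL and PRO instruments should be administered", they are absent from that section's pre-dose list, and Table 2 marks them only at 8 hours. That leaves 13 − 4 = 9 instruments with a pre-dose value. Section 12.5 limits the tests to continuous questionnaires, and C-SSRS is largely a yes/no form; without it there are 8. The synopsis also lists LEC-5 and PCL-5, but Table 1 schedules neither after dosing, so they add no test.

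**Step 2: scheduled post-baseline timepoints (Tables 1 and 2).**

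| Instrument | Timepoints |
|---|---|
| GAD-7, PHQ-9, BPI, C-SSRS | 6 each (8 hours, Days 2, 4, 8, 30, 90) |
| NIH HEALS | 4 (Days 2, 8, 30, 90) |
| POMS, SDS, AUDIT, DUDIT | 1 each |

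Total: 4 × 6 + 4 + 4 × 1 = 32 contrasts, or 32 − 6 = 26 without C-SSRS. Section 7.1.5 omits NIH HEALS from the Day 2 list although Table 1 marks it. Following the text would remove one contrast from each total, with little effect on the result.

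**Step 3: chance of at least one false positive, no true change anywhere.** For k independent tests it is 1 − 0.95^k. For correlated tests it was simulated with two-sided one-sample t-tests at n = 24 and a common correlation between all change scores. The protocol gives no correlations; 0.5 and 0.7 are assumptions.

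| Tests (k) | Independent | Correlation 0.5 | Correlation 0.7 |
|---|---|---|---|
| 8 (one per measure, no C-SSRS) | 1 − 0.95^8 = 33.7% | about 25–26% | about 20% |
| 9 (one per measure) | 1 − 0.95^9 = 37.0% | about 28% | about 21% |
| 26 (every visit, no C-SSRS) | 1 − 0.95^26 = 73.6% | about 49% | about 33–34% |
| 32 (every visit) | 1 − 0.95^32 = 80.6% | about 53–54% | about 35–36% |

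Simulated entries vary by about one percentage point between runs. The sample size does not drive these figures; the level and the number of tests do.

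**Step 4: the missing control arm.** Suppose a scale moves by d standard deviations of its change score for reasons unrelated to the drug. A two-sided one-sample t-test with n = 24 has 23 degrees of freedom and noncentrality d × √24. The values of d are assumptions.

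| d | Noncentrality | Chance that one measure is called significant |
|---|---|---|
| 0.3 | 1.47 | 29% |
| 0.4 | 1.96 | 47% |
| 0.5 | 2.45 | 65% |

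A modest non-drug drift on a single scale can thus matter as much as the multiplicity across all nine. No adjustment of the significance level would remove it.

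**The case against.** The other side has a fair case.

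- **The analyses are exploratory.** They are labelled so, and no primary or secondary conclusion depends on them. This stands. It is why the point is of low severity and why no multiplicity correction is asked for. It does not justify a significance verdict; it argues against one.
- **The SAP may settle it.** Section 12.5 is an outline. The model, the choice of contrast, a lead measure and any multiplicity handling are normal SAP content, and their absence is no fault here. This also stands. But the per-measure p<0.05 rule is in the protocol, and a SAP that treated the p-values as nominal would have to qualify it.
- **The confidence intervals are already planned.** True. What needs changing is the verdict beside them.

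Three stronger readings are tempting, and the documents do not support them.

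- A reader might infer that a false significant result is more likely than not. At one test per measure, which is what Section 12.5 states, the chance is at most about 37%. It passes 50% only if each visit is also tested and the correlation is not high. Section 4.4.3 leaves that open with "Mean changes from baseline to various study visit timepoints" but does not require it.
- A reader might add the wearable measures to the count. Their paragraph in Section 12.5 carries no p-value threshold.
- A reader might infer that a single significant scale will be presented as efficacy. No section says so.

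**Conclusion.** The concern holds for the one sentence in Section 12.5 that fixes a significance verdict for each continuous questionnaire. With no true change, at least one such verdict is expected in about 34–37% of trials at one independent test per measure, and in about 20–28% at assumed correlations of 0.7 to 0.5. Testing every scheduled visit would raise this to about 74–81% if independent and about 33–54% at those correlations. Even the lowest of these figures is about four times the nominal 5%.

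These figures rest on two-sided tests, 8 to 9 instruments with a pre-dose value, 26 to 32 scheduled contrasts, and assumed correlations. The second weakness is separate: in a single arm, a significant change from baseline could not be attributed to the drug even if it were real. Severity is low, and the primary safety objective is unaffected.

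**What to change.** Replace the significance sentence in Section 12.5 with:

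> Changes from baseline will be estimated with 95% confidence intervals; any p-values are nominal and exploratory, and no measure will be declared statistically significant or taken as evidence of a drug effect.

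No multiplicity correction is needed. A correction would deal with chance findings but not with the missing comparator, whereas dropping the verdict removes the misleading label in both cases.

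The cost is one sentence, with no change to data collection, visits or sample size. The downside is that individual scales can no longer be called significant in the report.

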
Description of Modifications: The eligible population of participants was refined to include PTSD patients and not only treatment resistant PTSD patients. In addition, the primary endpoints were clarified to be more precise and the liver as well as the kidney function adverse events were added.
 
Furthermore, the exploratory endpoints were clarified with the following psychiatric assessment and patient quality-of-life instruments added: Life Events Checklist for DSM-5 (LEC-5), PTSD Checklist for DSM-5 (PCL-5), Patient Health Questionnaire-9 (PHQ-9), NIH-HEALS, Profile of Mood States (POMS), Sheehan Disability Scale (SDS), 5-Dimensional Altered States of Consciousness Rating Scale (5D-ASC), Alcohol Use Disorders Identification Test (AUDIT), Drug Use Disorders Identification Test (DUDIT). The following instruments were added in the synopsis to be aligned with the protocol: Generalized Anxiety Disorder Scale (GAD-7), Brief Pain Inventory (BPI), Watts Connectedness Scale (WCS), Mystical Experience Questionnaire (MEQ30) – Revised, Challenging Experience Questionnaire (CEQ).
 
The following instruments were removed: Existential Distress Scale, Quick Inventory of Depressive Symptomatology, Self-Report (QIDS-SR16), Montgomery-Åsberg Depression Rating Scale (MADRS), EuroQoL-5 Dimensions-5 Levels questionnaire (EQ-5D-5L), Chronic-Pain Grade Scale (CGPS), Awe Experience Scale (AWE-S), Demoralization Scale (DS), Timeline Follow Back (TFLB), collectively.
 
Exploratory objectives and endpoints regarding the impact of psilocybin mushrooms on sleep outcomes, heart rate and heart rate variability during sleep, daily activity and means changes in epigenetic markers of psychiatric and cardiovascular related genes were also added.
 
Inclusion criteria were added such as acceptable renal and hepatic functioning.
 
Participants will also be provided with a provided with a health tracking wearable device to monitor several variables such as total daily steps, sleep parameters as well as heart rate and blood pressure. The electronic daily diary to record their physical and mental health was removed.
 
The product is administered as three 10 mg doses (30mg±10 %) instead of one 30mg dose (±5mg). All three units are administered concurrently during a single dosing session.
 
Other modifications included: alignment of the synopsis with the protocol, refinement of the Schedule of Events (SOE), adding a second SOE table that provides more detailed information to guide the timing of protocol-mandated activities on Study Day 1, confirmation of protocol-required activities across all study visits including the need to return to the study site multiple times during the Screening Period, and consistency in language and timing for eligibility criteria, deletion of mention of life-threatening cancer from previous protocol version.
 
In addition, timing of the post-eligibility confirmation one-to-one, group and ceremony activities as part of the Screening Period were established. And, the presence of a therapy dog, to provide emotional support also was incorporated.
 
A slight refinement of the generalized statistical approach was added; details regarding the precise statistical methods to be employed will be incorporated in the planned Statistical Analysis Plan. Lastly, the roles and responsibilities of the independent Data Safety Monitoring Board (DSMB) were clarified, including that the specific elements of what the DSMB will do will be incorporated into the planned DSMB Charter.
 
Other changes were editorial in nature and made throughout the document.
	

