3.3. Exploratory Objectives

- To evaluate the preliminary efficacy of psilocybin mushrooms.
- To assess changes in quality of life after taking psilocybin mushrooms.
- To evaluate the impact of psilocybin mushrooms on objective sleep outcomes (sleep duration, sleep latency, sleep efficiency) via a health tracking wearable device.
- To evaluate the impact of psilocybin mushrooms on heart rate and heart rate variability (HRV) during sleep via a health tracking wearable device.
- To evaluate the impact of psilocybin mushrooms on daily activity levels (i.e., steps) via a health tracking wearable device.
- To evaluate mean changes in epigenetic markers of psychiatric- and cardiovascular-related genes.

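### Section 12.5 appears to limit the heart-rate and HRV analysis to days not reported as unusual, which can bias the change if dosing alters how often such days occur or are reported

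*Protocol*

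**What the plan says.** The exploratory objective in protocol section 3.3 is "To evaluate the impact of psilocybin mushrooms on heart rate and heart rate variability (HRV) during sleep via a health tracking wearable device". Section 12.5 gives the analysis rule. Its stated reason is "As heart rate and heart rate variability are highly confoundable metrics", and the rule is that "analysis of these metrics will be done on all data collected but limited to days without unusual conditions reported by the participants". The examples of unusual conditions are "unusual alcohol consumption, changes in medication, very high activity, illness, death of a family member or other extraordinary stress unrelated to study participation".

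The rule has no time limit, so it covers days after the single dose as well as baseline days. Section 12.5 describes no separate analysis on all days. The bullet just before it says that change in sleep measures, nightly HRV and steps "from baseline (through product use) will be assessed". Section 6.5.1 gives one dosing session, and section 4.1 has the device returned at the Day 90 visit.

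**The concern.** Two things are wrong with the rule as written.

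First, it can be read in more than one way. Data cannot be both everything collected and a limited subset. The sentence may mean the whole collection period with flagged days removed, or two analyses side by side. The first is the plainer reading.

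Secondly, on that reading, post-dose days are selected by post-dose events, and the protocol treats several of these as things the drug may change:

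- Very high activity is a trigger, yet section 3.3 also sets the objective "To evaluate the impact of psilocybin mushrooms on daily activity levels (i.e., steps) via a health tracking wearable device".
- Unusual alcohol consumption is a trigger, yet AUDIT change from baseline is an exploratory endpoint in section 4.4.3.
- Medication change is a trigger, yet section 8.4 expects medications to be given for adverse events.
- Illness is a trigger, yet section 10.1 lists headache and nausea among the expected reactions.

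Only the stress item is limited to matters unconnected with the study. If dosing shifts how often flagged days occur, the part of the effect that acts through those days is lost from the estimate. The study has no control arm that would reveal such a shift.

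**Working it through.** **Inputs.** The protocol states no effect size, standard deviation or expected share of unusual days for heart rate or HRV, so there is no figure to reproduce. All values below are assumptions that show the mechanism.

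- g = mean shift in sleeping heart rate on a flagged night, taken as 3, 5 or 8 bpm and equal before and after dosing.
- p0, p1 = share of nights flagged before and after dosing.
- m0, m1 = mean heart rate on unflagged nights before and after dosing.

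**Formula.**

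- All-nights change = (m1 + g × p1) − (m0 + g × p0)
- Restricted change = m1 − m0
- Gap (all-nights minus restricted) = g × (p1 − p0)

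**Results (gap, bpm).**

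| g | 10% to 10% | 10% to 20% | 10% to 30% | 20% to 10% | 30% to 10% |
|---|---|---|---|---|---|
| 3 | 0 | +0.3 | +0.6 | −0.3 | −0.6 |
| 5 | 0 | +0.5 | +1.0 | −0.5 | −1.0 |
| 8 | 0 | +0.8 | +1.6 | −0.8 | −1.6 |

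For example, 8 × (0.30 − 0.10) = +1.6 and 3 × (0.10 − 0.20) = −0.3. The gap is zero when the share does not move.

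**When reporting depends on the participant's state.** A simulation used 24 participants, 21 baseline and 29 post-dose nights, g = 5 bpm, no direct drug effect and 2,000 replicates. With flagging independent of any other influence on heart rate it agrees with the formula. A rise from 10% to 30% gives +1.00 on all nights and 0.00 restricted; a fall from 30% to 10% gives −1.00 and 0.00. In a second version a daily state moves both heart rate and the chance of a flag. The rise then gives +0.98 on all nights and −0.32 restricted; the fall gives −0.99 and +0.31. In that version the restricted estimate has the opposite sign to the all-nights change, and it also misses the true direct effect of zero.

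The same formula holds for HRV with g in HRV units. The documents give nothing from which to set a plausible g, so no HRV figure is offered.

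**Can the flagged days be identified?** Section 8.4 has participants note alcohol, medications and health care use and hand this over at visits, with medication start and end dates recorded. Sections 7.1.5 to 7.1.7 add medication and adverse-event or health review on Days 2, 4 and 8. Alcohol and medication therefore have a partial record. Table 1 schedules no day-level record for very high activity or stress, and after Day 8 the only visits are Day 30 and Day 90. The device counts steps, but the rule depends on what participants report.

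**The period analysed.** Dosing takes place once, on Day 1, and the device is worn to Day 90. Read literally, a change measured through product use would end on the dosing day.

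**The case against.** The strongest defence is that the rule is deliberate and reasoned. Sleeping heart rate and HRV respond to illness, alcohol and bereavement. With up to 24 participants and no control arm, readmitting such nights brings in outside events that nothing in the design absorbs. An effect on ordinary days is also a coherent target. This stands, and it is a good reason to keep the restricted analysis. It does not justify a rule that ignores cause, or leaving the all-nights result unstated.

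A second defence is that the closing qualifier shows that only outside events are meant. That is probably the intent, and the stress item is safe for this reason. Grammatically the qualifier does not reach alcohol, medication, activity or illness.

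A third is that an analysis plan not shown here may define two analyses and the time windows. It may, but section 12.5 already states a restriction, and its wording needs repair wherever the detail sits.

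Three stronger readings are tempting and are not supported:

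- A reader might infer that the rule does bias the result. The documents say nothing about how often such days occur or whether dosing changes that.
- A reader might infer that flagged nights are certain to be the only ones excluded and the rest the only ones analysed. The wording is too ambiguous to establish this.
- A reader might infer that all flags rest on recall at Day 30 and Day 90, since the amendment summary says "The electronic daily diary to record their physical and mental health was removed". That describes a past change. Section 8.4 and the early contacts give a partial record for alcohol and medication.

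**Conclusion.** The concern holds in conditional form. Section 12.5 is ambiguous, and on its plain reading it removes post-dose days for reasons that the protocol elsewhere treats as possible drug effects. The estimated change can be biased in either direction if dosing alters the frequency or reporting of those days. The true size is unknown. The range of 0.3 to 1.6 bpm rests wholly on assumed shifts of 3 to 8 bpm and assumed share changes of 10 to 20 percentage points. A restricted result of exactly zero in the worked cases follows from assuming that the drug acts only through flagged nights; it is not a prediction.

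The reach is small. These are exploratory wearable measures, and the tachycardia and bradycardia adverse-event endpoints in section 4.4.1 are not subject to the rule. The change is still worth making, because it is cheap and makes any selection visible.

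**What to change.** In section 12.5:

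1. State that heart rate and HRV will be analysed on all recorded nights and, as a sensitivity analysis, on nights without reported unusual conditions.
2. Report the percentage of nights flagged before and after dosing.
3. Where the restriction is used, limit it to events judged unrelated to study treatment, for every item on the list.
4. Replace the reference to product use with a statement of the post-dose period covered.

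The cost is a few lines of wording and one extra table, with no new data collection. The all-nights estimate will be noisier and will include unrelated events such as illness or bereavement. The sensitivity analysis shows how much these matter. Which of the two leads is partly a matter of judgement in a single-arm study; the essential change is that both are reported.
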